## Study Objectives

The goal of this study is to determine the formation and kinetics of reactive carbonyl adducts of dietary flavonoids (soymilk, blueberry and green tea) in humans after a single dose of the dietary flavonoids. We speculate that the dietary flavonoids (soymilk, blueberry and green tea) can react with endogenous reactive carbonyls species to form reactive carbonyl adducts in the body, eventually alleviating the damaging effects of reactive carbonyls species on human health. Study on the formation and kinetics of reactive carbonyl adducts of dietary flavonoids is also expected to be able to provide substantial evidence for the health effects of regular dietary flavonoids (soymilk, blueberry and green tea) consumption in epidemiological studies.

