## Study Methods- Procedures

### 1. Dietary Flavonoids (Soymilk) Consumption and Placebo

#### Week 1 (Wash-in Period: Days 1-7)

Sixteen (16) healthy volunteers were recruited and instructed to avoid consuming soymilk, green tea, and blueberry products starting one week before the intervention and continuing throughout the entire three-week study period.

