#### Week 2 (First Intervention: Day 8)

Participants were randomized into two groups:

- **Soymilk-first group:** Consumed a breakfast including 460 mL of soymilk in a single dose.
- **Control-first group:** Consumed a breakfast including 460 mL of milk in a single dose.

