#### Biological sample collection:

- Urine and blood samples were collected at multiple time points over a 24-hour period.
- Fecal samples were collected at different time points over a 48-hour period.

Participants continued to avoid consuming soymilk, green tea, and blueberry products.

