#### Week 3 (Cross-over: Day 15)

Participants switched interventions:

- Those who previously consumed soymilk in Week 2 now consumed milk.
- Those who previously consumed milk in Week 2 now consumed soymilk.

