## Statistical Analysis Plan

The primary objective of this study is to evaluate whether dietary flavonoids from soy milk, blueberries and green tea can trap reactive carbonyl species in humans by detecting the formation of carbonyl adducts of these flavonoids.

Statistical Analysis: ANOVA with repeated measures and post hoc comparisons will be conducted to identify metabolites that show significant differences across various time points or treatments.

Power Analysis: A sample size of n=16 subjects per group will provide 80% power to detect metabolites with an effect size of 0.809, which is sufficient to assess the expected trapping effects of dietary flavonoids.

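### The SAP permits but does not require the product-versus-control comparison for the adduct-formation claim, and states no error control across adducts and matrices

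*Combined protocol and SAP*

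**What the plan says.** The Statistical Analysis Plan is one short section. It sets the primary objective as showing trapping by "detecting the formation of carbonyl adducts of these flavonoids". The analysis is a repeated-measures ANOVA with post hoc comparisons, used to "identify metabolites that show significant differences across various time points or treatments". The power statement gives 16 subjects per group and "80% power to detect metabolites with an effect size of 0.809". The section does not give an alpha, a primary adduct, matrix or time point, a deciding effect (time, treatment or their interaction), or an adjustment across tests.

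Study Objectives adds a descriptive aim, to "determine the formation and kinetics of reactive carbonyl adducts of dietary flavonoids", for which changes over time are the natural quantity.

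The design supplies a control. In the soymilk study half the comparison is a breakfast with milk ("Consumed a breakfast including 460 mL of milk in a single dose"), and on Day 15 the groups switch: "Those who previously consumed soymilk in Week 2 now consumed milk". The blueberry study uses sweet water and the green tea study uses water in the same way. For each product, "Urine and blood samples were collected at multiple time points over a 24-hour period", and feces over 48 hours.

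Background exposure is restricted. Participants were "instructed to avoid consuming soymilk, green tea, and blueberry products starting one week before the intervention", and this continued through the study. The inclusion criteria also bar flavonoid-enriched supplements, and any drugs or supplements within three weeks of the experiment.

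**The concern.** The claim that a product causes adducts to form needs a comparison with what happens without the product. Within this design, only the control period separates the product's effect from that of the rest of the breakfast, the time of day or another dietary source. The analysis sentence joins time points and treatments with an or, so a metabolite that changes equally after soymilk and after milk meets the criterion as well as one that changes only after soymilk. If such a metabolite were cited for the primary objective, the crossover would have gone unused on its main question.

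The lesser gap is error control. Several adducts may be tested in blood, urine and feces for each product. Post hoc comparisons, with no method named, would at most cover comparisons within one metabolite's ANOVA.

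**Working it through.** **1. The plan's own power figure.** Inputs from the SAP: n = 16, effect size 0.809, stated power 80%. Test and alpha are not given; I assume two-sided 5%. Read as a paired standardized difference, the noncentrality is 0.809 × √16 = 3.236. With 15 df (critical t 2.131) power is 85.6%; with 14 df, after a sequence or period term (critical t 2.145), it is 85.3%. Exactly 80% would correspond to 0.749. Two independent groups of 16 would give 60.1%. So 80% is not reproduced under these readings, but n = 16 does support one paired contrast. The point here does not depend on this figure.

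**2. Flag rates when the product has no effect.** The documents give no variances and no number of blood or urine time points. Assumed: participant share of variance 0.5, AR(1) errors with correlation 0.5, and 6 or 8 time points; the fecal calendar in Scheme 2 gives 3 (0, 24 and 48 h). Two treatments, 16 participants, each test at 5%. GG is Greenhouse-Geisser.

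| Rule | No change at all | Equal change of 0.25 SD in both periods |
|---|---|---|
| Time or treatment | 10–12% (GG 8–9%) | 19–47% (GG 13–43%) |
| Time, product period only | 5–8% (GG 4%) | about 11–24% (GG 5–22%) |
| Product-minus-control, period-adjusted AUC | 4–6% | 4–6% |
| Treatment-by-time | 5–8% (GG 3–5%) | 5–8% (GG 3–5%) |

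The first entry is close to what two independent 5% tests give, 1 − 0.95² = 9.75%; the excess comes from uncorrected non-sphericity. Varying the variance share from 0.3 to 0.7 and the autocorrelation from 0 to 0.7 moves it to 9–14% (GG 7–10%). The ranges in the last column reflect the number of time points and the shape of the curve. Entries there for the two time-based rules are detections of a real time change; they become errors only if read as formation caused by the product.

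**3. Several tests per product.** One adduct in three matrices, each at 5%: 1 − 0.95³ = 14.3% if independent; by simulation 13% at a correlation of 0.5 between matrices and 10% at 0.8. With five adducts (an assumed number) in three matrices, 15 tests: 1 − 0.95¹⁵ = 53.7%, falling to 49% and 41%.

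**4. What adjustment costs in power.** At 0.809 with 14 df, Bonferroni over 3, 10 and 15 tests gives 69%, 49% and 43%. Benjamini-Hochberg does better when more effects are real: with 3 tests, 71%, 78% and 84% when 1, 2 or 3 are real; with 15 tests, 44%, 55%, 64% and 83% when 1, 3, 5 or 15 are real.

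**The case against.** The strongest reply is that the objective and the ANOVA are in separate sentences, and that no text equates a significant time effect with trapping. That stands. A reader might infer that the plan would declare trapping for every flagged metabolite, or that it omits the treatment comparison. The documents support neither: they describe metabolites to be identified, and treatments are named in the criterion. The defect is that the comparison is not required.

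It can also be said that adducts of soy, blueberry or tea flavonoids should hardly appear in a control period after a week without those foods and with flavonoid-enriched supplements barred. This makes a shared change less likely, and nothing in the documents shows that one occurs. It does not rule one out. Other foods containing flavonoids, and the rest of the breakfast, are not addressed in the readable text, and the plan states no detection rule that relies on absence under control. The 19–47% range should therefore not be read as an expected error rate.

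Finally, time changes are legitimate evidence for the kinetics aim, and an adduct absent before dosing and after control but present after the product does bear on formation. Both are right; the second is itself a comparison with control, and the fix keeps both.

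**Conclusion.** The concern holds as a gap in specification that should be fixed, not as a stated wrong inference. The formation claim is not tied to the product-minus-control contrast, and no error control is given across adducts and matrices within a product. With no product effect and no shared change, the time-or-treatment criterion flags roughly twice as many metabolites as the contrast (10–12% against about 5%). Anything beyond that rests on a shared change of unknown size. The family-wise figure for one adduct in three matrices is at most about 14% per product if the tests are independent or positively correlated. Both sets of figures assume tests at 5%; the flag rates also rest on the assumed variances and sampling times. Confidence is high in the omission and moderate in its practical consequence.

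**What to change.** Suggested SAP text:

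> For each product, formation of an adduct in a given matrix is claimed only if the within-participant product-minus-control contrast, from a model with period and sequence terms, is significant with the higher level after the product. Benjamini-Hochberg control at 5% applies over all adducts and matrices tested for that product. Claims are made for each adduct in each matrix. Time changes within the product period are reported as kinetics and do not establish formation without the control comparison.

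Use one summary per matrix that the collected samples support: for example AUC 0–24 h for blood, cumulative amount for urine only if volumes or complete collections were recorded (otherwise a concentration summary), and a baseline-corrected 0–48 h level for feces. A Greenhouse-Geisser-corrected treatment-by-time interaction, followed by a check that the level is higher after the product, is an acceptable alternative.

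State how values below detection are handled. An adduct undetected before dosing and after control but detected after the product may count through a paired comparison of detection, such as exact McNemar, within the same family. Before adjustment this needs at least six discordant participants, all in one direction (2 × 0.5⁶ = 0.031; with five, 2 × 0.5⁵ = 0.063).

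Two checks come first. Confirm that both sequences were run: the procedures describe both, while the Scheme 2 calendar shows Day 8 as control and Day 15 as treatment, which may be one sequence's calendar. Because the procedures are in the past tense and the calendar is dated 2023, disclose it if the rule was fixed after data were seen.

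The cost is wording and a little analysis, with no new samples for blood or feces. Fewer metabolites will be called significant. Reading 0.809 as a paired standardized difference, power is about 85% for a single contrast and at least 69% with three tests.

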**Scheme 1. Recruitment, screening, and enrollment for each PK study**

## Scheme 2. Experimental design and sample collections of the acute PK study with a crossover design

| Calendar for Fecal Sample Collection_Human Study_2023   |   |   |  |       |               |               |
|---|---|---|--|-------|---------------|---------------|
| Day 0 (Consenting)  | Day 1   | Day 2   | Day 3  | Day 4 | Day 5         | Day 6         |
| Day 7 
 
○ Pick up cooler and fecal collector;
 
    | Day 8 (Control) 
 
○ Collect baseline (0 h) fecal samples;
 
○ Bring baseline fecal sample to HRC;
 
○ Pick up another cooler and fecal collector;
 
○ Collect 24-h fecal samples;
 
 | Day 9 
 
○ Bring 24-h fecal sample to HRC;
 
○ Pick up another cooler and fecal collector;
 
○ Collect 48-h fecal samples;
 
  | Day 10 
 
○ Bring 48-h fecal sample to HRC;
 
○ Pick up another cooler and fecal collector;
 
 |       | Day 11 | Day 12 |
| Day 14 
 
○ Collect baseline (0 h) fecal samples;
 
 | Day 15 (Treatment) 
 
○ Bring baseline fecal sample to HRC;
 
○ Pick up another cooler and fecal collector;
 
○ Collect 24-h fecal samples;
 
   | Day 16 
 
○ Bring 24-h fecal sample to HRC;
 
○ Pick up another cooler and fecal collector;
 
○ Collect 48-h fecal samples;
 
 | Day 17 
 
○ Bring 48-h fecal sample to HRC;
 
  |       | Day 18 | Day 19 |
|   |   |   |  |       |               | Day 20 |

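### The SAP gives the 0 h stool sample no baseline role; if 0 h is averaged into the treatment main effect, the fecal product effect shrinks by exactly one third

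*Combined protocol and SAP*

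**What the plan says.** The analysis section of the SAP is one sentence: "ANOVA with repeated measures and post hoc comparisons will be conducted", in order to "identify metabolites that show significant differences across various time points or treatments". The two sources of variation named are time and treatment. The sentence does not say which sampling times enter the model, whether any value serves as a baseline, or whether the product effect is judged by the treatment main effect, the treatment-by-time interaction or comparisons at single times.

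The Scheme 2 calendar lists three stool samples in each period: "Collect baseline (0 h) fecal samples" (under Day 8 in the first period and Day 14 in the second), "Collect 24-h fecal samples" and "Collect 48-h fecal samples". The Procedures text is less specific: "Fecal samples were collected at different time points over a 48-hour period". For the other matrices it says only "Urine and blood samples were collected at multiple time points over a 24-hour period", with neither the number of times nor a pre-dose sample stated in the readable text.

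**The concern.** The 0 h stool is a baseline, so its expected product-minus-control difference is zero. A treatment comparison that averages over all three times therefore mixes one value that cannot respond with two that can. The 0 h value does carry each participant's level in that period, and the difference in level between periods is noise in a crossover comparison. Using 0 h as a covariate can remove part of that noise; using it as a response level in the main effect does not.

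Each product is tested in 16 people. Several analyses fit the SAP sentence and differ materially in power, so leaving the choice open also allows it to be made after the results are seen.

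**Working it through.** **Inputs.** From the documents: 16 participants per product, effect size 0.809, claimed power 80%, stool at 0, 24 and 48 h in each period. Assumed, because not given: two-sided 5% test, no dropout, no carryover or period effect, equal effect at 24 h and 48 h, common correlation *r* between the paired differences at any two times, and SD 1 for each of them (varied for 0 h in step 4).

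**1. The plan's own power figure.** If 0.809 is in SD units of a paired difference, the noncentrality is 0.809 × √16 = 3.236 on 15 df and power is 85.6%. For two independent groups of 16 it is 0.809 × √8 = 2.288 on 30 df and power is 60.0%. Neither gives 80%, and the SAP names no test, alpha or SD. The paired reading is used below because it fits the crossover. The present point does not depend on resolving that gap.

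**2. Dilution.** With product-minus-control effects 0, d24 and d48, the treatment main effect is

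(0 + d24 + d48)/3 = (2/3) × (d24 + d48)/2.

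This is two thirds of the post-dose mean effect for any 24/48 h profile. With 0.809 at both times it is 0.539. With T times, one of them pre-dose, the loss is 1/T. It cannot be computed for blood or urine because T is not stated.

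**3. Power with equal SD at all times.**
- Main effect over 0, 24 and 48 h: SD = √((1 + 2r)/3), so the standardised effect is 0.539/SD = 0.934, 0.790, 0.661, 0.603 at r = 0, 0.2, 0.5, 0.7.
- Mean of 24 h and 48 h: SD = √((1 + r)/2), so 0.809/SD = 1.144, 1.044, 0.934, 0.877.
- The same mean adjusted for the 0 h difference: residual variance (1 + r)/2 − r² = 0.50, 0.56, 0.50, 0.36.

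The first two columns below follow from the noncentral t on 15 df. The last two come from simulation with at least 20,000 trials per scenario.

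| r | Main effect including 0 h | Post-dose mean, no covariate | Post-dose mean, 0 h covariate | Treatment-by-time interaction |
|---|---|---|---|---|
| 0 | 94% | 99% | 98% | 61% |
| 0.2 | 84% | 97% | 97% | 71% |
| 0.5 | 69% | 94% | 98% | 90% |
| 0.7 | 62% | 91% | 100% (rounded) | 99% |

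At r = 0 and 0.2 the whole gain over the main effect comes from leaving 0 h out of the average. At r = 0.5 and 0.7 the covariate adds 4 and 9 points more. A single comparison at 24 h or at 48 h has 86% power at any r, before multiplicity adjustment. Type I error is about 5% for these tests.

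At a smaller assumed effect of 0.6, which is not in the documents, the main effect has about 74/59/45/39% and the covariate analysis 86/82/86/95%.

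**4. Power when 0 h is nearly constant.** Set the SD of the 0 h difference to 0.1. The SD of the three-time mean becomes √((2.01 + 2.4r)/9). At 0.809, main-effect power is 99/97/92/88%, against 99/97/94/91% for the unadjusted post-dose mean, a loss of at most about 3 points. In the limit of a constant 0 h, estimate and standard error both shrink to two thirds and the t statistic does not change. The covariate analysis still gives 98/97/98/100%, because its gain depends on r and not on the size of the 0 h SD.

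**The case against.** A reader might infer that the SAP states that 0 h is a response level. It does not. It is silent, and a sponsor could subtract 0 h, adjust for it or drop it without contradicting the text. The inference is natural only because 0 h is a time point and nothing removes it.

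A reader might also infer that every product-versus-control comparison loses power. That fails too: a post hoc comparison at 24 h or 48 h contains no 0 h value, and the interaction is not diluted by averaging. Nor is the baseline simply wasted, since the interaction and the time contrasts use 0 h as their reference. What remains is that none of these adjusts for 0 h as a covariate. In step 3 none exceeds the covariate analysis, although the interaction comes close at r = 0.7.

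The strongest objection concerns the equal-SD assumption. The outcome is adducts of the test flavonoids, and 0 h follows a week without the three products. Low and nearly constant 0 h values are plausible, although other flavonoid foods are not restricted. Step 4 shows that the dilution then costs little power. This stands as a limit on the size of the concern. It does not restore the estimate, which is still two thirds of the post-dose effect, and it does not settle which contrast is intended.

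Extending the one-third figure to blood or urine is not supported, because a 0 h sample is documented only for stool.

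**Conclusion.** The point holds as a gap with a cheap improvement, not as a demonstrated error. The SAP assigns no baseline role to a 0 h stool that the calendar collects in each period, and it does not name the contrast that tests the product. If 0 h is averaged in, the fecal main effect is exactly two thirds of the post-dose effect; this needs only a zero expected difference at 0 h. The power cost is conditional. At 0.809 with equal SDs, the main effect falls short of the covariate analysis by about 4, 13, 29 and 38 points at r = 0, 0.2, 0.5 and 0.7. With a near-constant 0 h, the cost of dilution itself is at most about 3 points, and any further gain from the covariate rests on a correlation that the documents do not give. Validity under the null is not in question.

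**What to change.** State in the SAP that, for each adduct, the product-versus-control contrast uses post-dose samples only (24 h and 48 h for stool), with each period's own 0 h value as covariate. In 2x2 terms, regress the post-dose product-minus-control difference on the 0 h product-minus-control difference and test the intercept. Apply this to feces and to any other matrix that has a 0 h sample. Omit the covariate for adducts that are non-detect at 0 h in everyone. If the sponsor intends another use of 0 h, the SAP should say which.

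The cost is a few lines of SAP text and no new samples. The covariate uses one degree of freedom. When 0 h is uninformative (r = 0) this costs about 2 points of power at an assumed effect of 0.6 (88% unadjusted against 86%) and about 1 point at 0.809 (99% against 98%).
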